### 2.3.2 Protocol Deviations

Subjects with any protocol deviations will be summarized by treatment group, overall, by site, and by type. Subjects with out-of-window visit protocol deviations will be presented by visit and number of days out of window for each treatment group and overall.

Depending on the seriousness of a protocol deviation, a subject might be excluded from the PP population, which shall be documented prior to database lock. Since the PP population includes subjects who complete the visit 9 months after baseline, the focus will be on major deviations occurring before and at the Month 9 visit which are considered to have a substantial impact on the primary effectiveness outcome, see Table 3 below for list. Reasons for exclusion from the PP population also will be summarized.

 GALDERMA EST. 1981	Title 43USSA2112 Statistical Analysis Plan - Sculptra Decolletage US Pilot	Doc id MA-55694
---	--	---------------------------

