3.6.1 Emergency unblinding

Not applicable as the treating Investigator is not blinded to treatment.

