9.9 Withdrawals and deviations

All withdrawn subjects will be listed individually, including at least subject number, date and reason for withdrawal, and last visit performed.

Subjects with CIP deviations will be listed individually, including subject number and observed deviation. Depending on the seriousness of the deviation, the subject may be excluded from the PP population, which shall be documented prior to database lock (DBL).

	Title 43USSA2112 CIP Sculptra Decolletage	Doc id
GALDERMA EST, 1981		MA-50966

Deviations from the statistical plan will be documented in the Clinical Study Report (CSR). If the statistical plan needs to be changed before DBL, but after the finalization of the SAP, the SAP will be amended.

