#### 1.1.1 Study Design

This is a prospective open-label study to evaluate the safety and effectiveness of *Sculptra* for correction of wrinkles in the décolletage area.

Approximately 30 subjects will be enrolled in the study and randomized 1:1 to receive either *Sculptra* reconstituted with 8 mL Sterile Water For Injection (SWFI) with the addition of 1 mL 2% lidocaine hydrochloride (HCl) or *Sculptra* reconstituted with 17 mL SWFI with the addition of 1 mL 2% lidocaine HCl. Subjects will be stratified by Galderma Décolletage Scale (GDS) severity score (moderate or severe) and study center.

Eligible subjects will perform a screening visit and baseline visit; these visits may be combined, if appropriate. Eligible subjects will be offered treatment with *Sculptra* in four sessions spaced one month (+2 weeks) apart.

Subjects will be injected with *Sculptra* by the Treating Investigator at Baseline. Sufficient amount of product, as determined by the Treating Investigator, should be injected to achieve optimal correction, which is defined as at least a one grade improvement on the GDS and best correction that could be achieved as agreed upon by the Treating Investigator and the subject. Three additional treatment sessions may be performed if needed to achieve optimal correction, as determined by the Treating Investigator and subject. Treatment will stop when optimal correction has been achieved and subsequent visits will be follow-up visits.

CCI

[REDACTED] Safety follow-up assessments will also be conducted one month after each treatment (Visits 3a, 4a, 5a and 6). Safety and effectiveness data will be collected for up to 9 months following the initial treatment.

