#### 1.1.2 Number of Subjects and Randomization

Approximately 30 adult female subjects will be randomized 1:1 to receive either *Sculptra* reconstituted with 8 mL SWFI with the addition of 1 mL 2% lidocaine HCl or *Sculptra* reconstituted with 17 mL SWFI with the addition of 1 mL 2% lidocaine HCl. Subjects will be stratified by GDS severity score and study center. Randomization numbers will be allocated in ascending sequential order to each subject.

	Title 43USSA2112 Statistical Analysis Plan - Sculptra Decolletage US Pilot	Doc id MA-55694
--	--	---------------------------

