**Table 3. Major Protocol Deviations Causing Exclusion from Per-Protocol Population**

Major Deviation
Month 9 visit out of window by greater than 21 days or earlier than 7 days
Subject did not receive treatment as randomized
GDS live assessment by Treating Investigator not done at Month 9 (primary endpoint)
GDS live assessment by Treating Investigator not done at screening or baseline
GDS live assessment by Treating Investigator at baseline is not grade 2 or 3 (moderate or severe)
Prohibited concomitant treatments/procedures prior to Month 9 visit considered to have substantial impact on primary effectiveness outcome
Prohibited medical history, unstable medical history condition, or medical history condition that worsens prior to Month 9 visit considered to have substantial impact on primary effectiveness outcome

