## 2.7 Determination of Sample Size

### 2.7.1 Sample Size

The sample size of approximately 30 subjects is not based on a statistical calculation. **CCI**  
[REDACTED]

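### Two of the seven per-protocol exclusion criteria turn on a judged effect on the outcome, and in this open-label study nothing requires that judgement to be made without sight of arm and response

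*SAP*

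**What the plan says.** **Exclusion rule.** SAP 2.3.2 states that, according to how serious a deviation is, "a subject might be excluded from the PP population, which shall be documented prior to database lock". Protocol 9.9 is to the same effect: "Depending on the seriousness of the deviation, the subject may be excluded from the PP population", again documented before lock. SAP 2.3.2 then refers to Table 3 for the list of major deviations.

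**Table 3.** There are seven entries. Five are factual: Month 9 visit too far out of window, not treated as randomized, no Month 9 GDS, no screening or baseline GDS, and baseline GDS not grade 2 or 3. Two depend on impact. One reads "Prohibited concomitant treatments/procedures prior to Month 9 visit considered to have substantial impact on primary effectiveness outcome". The other applies the same qualifier to prohibited, unstable or worsening medical history.

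**Masking.** SAP 1.1.1 says "This is a prospective open-label study". Protocol 3.6 gives blinding as not applicable, and 3.6.1 adds "Not applicable as the treating Investigator is not blinded to treatment". That investigator scores GDS live at all visits (SAP 1.3.1), including the Month 9 primary endpoint (SAP 1.2.1).

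**Role of PP.** ITT is primary for all effectiveness analyses (SAP 2.4.1), with BOCF for a missing primary endpoint (SAP 2.4.2). PP is a repeat of the primary analysis, run only if enough subjects drop out of it. SAP 2.2.3 sets that condition as PP below 90% of ITT. SAP 2.4.1 and protocol 9.2 set it as a difference of at least 10%.

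**The concern.** Fixing PP membership before database lock protects the analysis when lock comes before unblinding: whoever decides does not yet know the arm. Here there is no unblinding step, so lock provides a date and a record but does not separate the decision from the data.

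That matters most for the two impact items. They ask whether a deviation substantially affected the primary outcome, and that question is hard to answer neutrally with the subject's Month 9 grade in view. The same deviation can look important in a non-responder and trivial in a responder. The word *might* in SAP 2.3.2 adds to this, because it leaves unclear whether Table 3 is binding and whether it is complete.

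At stake is the credibility of the plan's only re-analysis based on deviations. The other sensitivity analyses in SAP 2.4.2 (observed cases, worst case, best case) deal with missing data.

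**Working it through.** **Inputs.** N = 30, taking the planned number as exact; of it the SAP (2.7.1) says "The sample size of approximately 30 subjects is not based on a statistical calculation". Allocation is 1:1 (SAP 1.1.2), so 15 per arm. The documents give no expected responder rate, so 60%, 70% and 80% are assumptions. Intervals are two-sided 95% Clopper-Pearson, the method in SAP 2.4.3. The plan has no figure of its own to reproduce on this point.

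**Step 1: when PP is run.** Let k be the number excluded, and take the 10% relative to ITT.
- SAP 2.2.3: (30 − k)/30 < 0.90, so k ≥ 4.
- SAP 2.4.1: k/30 ≥ 0.10, so k ≥ 3.
- At k = 2, 28/30 = 93.3%, and neither rule triggers.
- At k = 3, 27/30 = 90.0% exactly. SAP 2.4.1 triggers and 2.2.3 does not.

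The two rules therefore disagree at three exclusions. Near that boundary, one judged exclusion can decide whether a PP result appears.

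**Step 2: how far selection can move the pooled PP rate.** With x responders among n subjects, excluding k non-responders gives x/(n − k), and excluding k responders gives (x − k)/(n − k). The spread is k/(n − k), whatever x is. For k = 3 it is 3/27 = 11.1 points.

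| Assumed rate | ITT | Three non-responders out | Three responders out |
|---|---|---|---|
| 60% | 18/30 = 60.0% (40.6 to 77.3) | 18/27 = 66.7% (46.0 to 83.5) | 15/27 = 55.6% (35.3 to 74.5) |
| 70% | 21/30 = 70.0% (50.6 to 85.3) | 21/27 = 77.8% (57.7 to 91.4) | 18/27 = 66.7% (46.0 to 83.5) |
| 80% | 24/30 = 80.0% (61.4 to 92.3) | 24/27 = 88.9% (70.8 to 97.6) | 21/27 = 77.8% (57.7 to 91.4) |

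At 80%, the shift from ITT is +8.9 points one way (88.9 − 80.0) and −2.2 the other (77.8 − 80.0).

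**Step 3: four exclusions, where both rules trigger.** Start with 12/15 = 80.0% in each arm. Excluding two non-responders from one arm gives 12/13 = 92.3%; excluding two responders from the other gives 10/13 = 76.9%. Equal arms then differ by 2/13 = 15.4 points.

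These are extreme cases: every exclusion comes through the two impact items, and selection on outcome is complete. They bound the effect and do not predict it. The ITT figures do not move in any of them.

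**The case against.** The strongest reply is that this is a supportive analysis in a small descriptive pilot, mostly governed by a pre-specified list. Much of that stands.

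- **Table 3 constrains most exclusions.** A reader might infer that PP membership as a whole is discretionary. It is not: five of the seven items are factual and listed in advance.
- **The decider is not identified.** A reader might infer that whoever decides certainly sees arm and Month 9 GDS, or that the result will be steered. The documents do not say so. They show that the treating investigator is unblinded, and they name nobody for the PP decision. Access on the sponsor side is plausible: the sponsor is told of prohibited therapy (protocol 3.8.4), and the sponsor or its representatives review eCRF data (10.3.1). That remains an inference. The defect is that the plan does not prevent such access.
- **PP is not the only check on deviations.** Deviations are summarized by group, site and type, and reasons for PP exclusion are summarized (SAP 2.3.2). Subjects with deviations are listed individually (protocol 9.9). Selective exclusion would leave a visible trace. PP is, however, the only re-analysis that acts on deviations.
- **The primary result is not at risk.** ITT with BOCF does not depend on PP membership. The primary analysis is a rate with an interval, and the readable text sets no success threshold.

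The reply does not answer the narrow point. A visible exclusion can still have been chosen with the response known, and the plan contains no step that rules this out for the two impact items.

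**Conclusion.** The concern holds in a limited form. Two of the seven Table 3 criteria rest on judged impact on the outcome, the surrounding wording is permissive, and documentation before lock does not mask those decisions in an open-label study. At N = 30, three fully selective exclusions can place the pooled PP rate anywhere within an 11.1-point range, for example 77.8% to 88.9% around an assumed ITT rate of 80.0%. That is smaller than the width of the ITT interval (61.4 to 92.3), but large enough to make the PP result look like support or like doubt.

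The effect is confined to a conditional, supportive analysis. The separate mismatch between the two PP triggers at exactly three exclusions follows from the SAP text and N = 30 alone. The sizes rest on N being exactly 30, equal arms where arms are shown, assumed responder rates and worst-case selection. This is a cheap improvement worth making; it does not threaten the primary conclusion.

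**What to change.** Amend the SAP before database lock, as its section 2.1 allows.

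1. **SAP 2.3.2:** state that Table 3 is binding and exhaustive, replacing the permissive wording.
2. **Five factual items:** apply them from programmed yes/no flags (for example, treated as randomized; Month 9 GDS done), so that nobody needs to see the arm or the grade to apply them.
3. **Two impact items:** have a named sponsor role decide them from a deviation listing without treatment group, post-baseline GDS or GAIS values, or photographs. The decisions are signed and dated before database lock.
4. **Optional, for prohibited therapies:** assess against the full list in protocol 3.8.4. A trigger restricted to procedures in the décolletage area would miss entries that extend beyond it, such as breast surgery or participation in another interventional study.
5. **Triggers:** align SAP 2.2.3 with 2.4.1. Using the at-least-10% rule in both, with ITT as denominator, also matches protocol 9.2.

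The cost is one extra masked listing, a few derived flags and slightly less case-by-case discretion. No new data are needed. The medical-history item remains a judgement, but one made without the outcome in view.

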**Table 3. Major Protocol Deviations Causing Exclusion from Per-Protocol Population**

Major Deviation
Month 9 visit out of window by greater than 21 days or earlier than 7 days
Subject did not receive treatment as randomized
GDS live assessment by Treating Investigator not done at Month 9 (primary endpoint)
GDS live assessment by Treating Investigator not done at screening or baseline
GDS live assessment by Treating Investigator at baseline is not grade 2 or 3 (moderate or severe)
Prohibited concomitant treatments/procedures prior to Month 9 visit considered to have substantial impact on primary effectiveness outcome
Prohibited medical history, unstable medical history condition, or medical history condition that worsens prior to Month 9 visit considered to have substantial impact on primary effectiveness outcome

### 2.3.3 Demographic Characteristics

Age and body mass index will be summarized as continuous variables.

Gender, race (including Asian subgroups), ethnicity, Fitzpatrick Skin Type (FST) score, childbearing potential, cup size, and baseline GDS (Treating Investigator) will be summarized as categorical variables.

### 2.3.4 Medical History, Medications, and Procedures

Prior and concomitant medications, vaccines, and procedural anesthetics will be coded using the World Health Organization Drug Dictionary (WHODD). Medical history, prior cosmetic treatments/procedures, and concomitant procedures/treatments will be coded according to the Medical Dictionary for Regulatory Activities (MedDRA).

Prior medications/procedures are the medications/procedures with stop dates prior to first study treatment session. Medications/procedures after the first study treatment session will be considered concomitant.

Subjects reporting medical history, prior cosmetic treatments/procedures, and concomitant procedures/treatments will be summarized by System Organ Class (SOC) and Preferred Term (PT). Procedural anesthetics will only be listed.

Subjects reporting concomitant medications and vaccines will be summarized separately, by WHODD Anatomical Therapeutic Chemical (ATC) Class Level 3 (if Level 3 is not available, the highest class available will be used) and WHODD preferred name. Prior medications will only be listed.

## 2.4 Effectiveness Analysis

### 2.4.1 Datasets Analyzed

The ITT population is primary for all effectiveness analyses. The primary effectiveness analysis will be repeated using the PP analysis population if there is at least a 10% difference in the number of subjects between the PP and ITT populations.

 GALDERMA EST. 1981	Title 43USSA2112 Statistical Analysis Plan - Sculptra Decolletage US Pilot	Doc id MA-55694
---	--	---------------------------

#### 2.4.2 Handling of Missing Data

Number of missing values will be summarized and reported as appropriate.

For the ITT analysis of the Treating Investigator GDS Responder rate at Month 9 after baseline (primary endpoint), missing values will be assumed to be missing due to lack of effect. Therefore, the primary method of imputation will use the baseline observation carried forward (BOCF) method. Impact of missing data on the primary endpoint will be evaluated by performing sensitivity analysis based on the observed cases, as well as worst-case and best-case imputation in the ITT set.

All other effectiveness endpoints will be evaluated based on the observed cases in ITT.

Descriptive statistics of all safety data will be performed on observed cases in the Safety population.

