### 1.2.2 Secondary Effectiveness Objectives and Endpoints

To evaluate the effectiveness of *Sculptra* for correction of wrinkles in the décolletage area the following endpoints will be used:

1. Percentage of responders, defined by at least one grade improvement from baseline, on the GDS, as assessed live by the Treating Investigator, at Month 6.
2. Percentage of responders, defined by having at least “Improved” (improved, much improved or very much improved) according to the Global Aesthetic Improvement Scale (GAIS), as assessed by the subject and the Treating Investigator separately, at Month 6 and 9.

CCI

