## 2.1.2 Reporting Conventions

The formats for the tables, listings, and figures described in this SAP will be provided in a companion document. Changes to the formats of these reports that are decided after the finalization of the SAP will not require an amendment. In addition, any additional supportive or exploratory analyses requested after SAP approval will not require amendment of the SAP. These additional analyses will be described in the CSR.

Study data from the eCRFs as well as derived variables will be provided in subject data listings. An indication of specific listings for each data type will not be indicated in the text of subsequent SAP sections. Data listings supplied as part of the CSR will be sorted by study site number concatenated with subject number, treatment group, assessment dates, and/or time point.

The following conventions will be applied to all data presentations and analyses:

- Confidence intervals (CIs) will be two-tailed and constructed at a confidence level of 95%. Statistical tests will be performed at a significance level of 5%, and p-values will be two-sided, unless otherwise specified.
- Quantitative variables will generally be summarized by the number of subjects, mean, standard deviation, median, minimum, and maximum. Unless otherwise specified, the minimum and maximum values will be displayed to the same number of decimal places as the raw data, the mean and median will be presented to one extra decimal place compared to the raw data, and the standard deviation will be displayed to two extra decimal places compared to the raw data.
- Categorical variables will be summarized by the number and percentage of subjects (and number of events where appropriate) within each category. Unless otherwise specified, the percentage will be presented in parentheses to one decimal place. Frequency and percentage values of 0 will be presented as '0' rather than '0 (0)'.
- All summary tables will include the analysis population sample size (i.e., number of subjects) in each treatment group.
- Date variables will be formatted as DDMMMYYYY for presentation.

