### 2.2.2 Intent-to-Treat (ITT) Population

The ITT population includes all subjects who were randomized, and will be analyzed according to the randomization scheme. All effectiveness variables will be analyzed based on the ITT population.

 GALDERMA EST. 1981	Title 43USSA2112 Statistical Analysis Plan - Sculptra Decolletage US Pilot	Doc id MA-55694
---	--	---------------------------

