#### 2.4.3 Primary Effectiveness Analysis

Responder rate for each treatment based on the GDS, as assessed live by the Treating Investigator at 9 months after baseline, will be the primary effectiveness endpoint. A responder will be defined as a subject with at least 1 grade improvement from baseline. The response rate will be calculated and presented with the 95% confidence intervals (calculated via Clopper-Pearson) for each treatment group and overall.

[figure not shown]

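### A missing Month 9 GDS counts as non-response, but Month 6 GDS and all GAIS responder rates use observed cases only, with no missing-as-failure check

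*SAP*

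**What the plan says.** SAP 2.4.2 and Protocol 9.6 give the same two rules.

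- **Primary endpoint (Treating Investigator GDS responder, Month 9).** In the ITT analysis, "missing values will be assumed to be missing due to lack of effect". The baseline observation is carried forward, which means no change and so no response. Observed-case, worst-case and best-case sensitivity analyses are planned for this endpoint only.
- **All other effectiveness endpoints.** "All other effectiveness endpoints will be evaluated based on the observed cases in ITT". No sensitivity analysis of these endpoints appears in the readable text.

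The second rule covers five secondary responder rates listed in SAP 1.2.2: GDS at Month 6, and GAIS "as assessed by the subject and the Treating Investigator separately, at Month 6 and 9". SAP 2.2.2 defines the population for all of them: "The ITT population includes all subjects who were randomized". SAP 2.4.4 also plots GAIS responder percentages by visit. SAP 2.4.2 provides for missing values to be counted and reported.

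**The concern.** GDS and GAIS are collected at the same final visit (Protocol 8.13). A subject who misses that visit misses both for the same reason, yet the plan reads her absence as failure on one scale and ignores it on the other. No reason is given for confining the lack-of-effect assumption to a single endpoint. GDS is also the same scale, rater and responder definition at Months 6 and 9, but its missing-data rule changes between the two visits.

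The study is a pilot whose data are meant to support a pivotal study (Protocol 1.2 and 3.2). Someone comparing endpoints or time points from the headline tables would be looking partly at the difference between two imputation rules.

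**Working it through.** **Inputs from the documents.** "Approximately 30 subjects will be enrolled in the study and randomized 1:1" (SAP 1.1.1), so N is about 15 per arm and 30 overall. Intervals are two-sided 95% Clopper-Pearson (SAP 2.1.2, 2.4.3, 2.4.4). There is no planned figure to reproduce: "The sample size of approximately 30 subjects is not based on a statistical calculation", and no response or dropout rate is stated.

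**Assumptions.** Missing counts m of 1 to 3 per arm (1 to 6 overall), and observed responder rates of about 60%, 80% and 90%.

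**Formulas.** With x observed responders, the observed-case rate is x/(N − m) and the missing = non-responder rate is x/N. The gap is x/(N − m) − x/N = [x/(N − m)] × (m/N), that is, the observed rate times the fraction missing.

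**One arm, N = 15**

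| Observed rate about | m | Observed cases | Missing = non-responder | Gap (points) |
|---|---|---|---|---|
| 60% | 1 | 8/14 = 57.1% | 8/15 = 53.3% | 3.8 |
| 60% | 2 | 8/13 = 61.5% | 8/15 = 53.3% | 8.2 |
| 60% | 3 | 7/12 = 58.3% | 7/15 = 46.7% | 11.7 |
| 80% | 1 | 11/14 = 78.6% | 11/15 = 73.3% | 5.2 |
| 80% | 2 | 10/13 = 76.9% | 10/15 = 66.7% | 10.3 |
| 80% | 3 | 10/12 = 83.3% | 10/15 = 66.7% | 16.7 |
| 90% | 1 | 13/14 = 92.9% | 13/15 = 86.7% | 6.2 |
| 90% | 2 | 12/13 = 92.3% | 12/15 = 80.0% | 12.3 |
| 90% | 3 | 11/12 = 91.7% | 11/15 = 73.3% | 18.3 |

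For 12/13 the Clopper-Pearson interval is 64.0% to 99.8%; for 12/15 it is 51.9% to 95.7%. Overall (N = 30), the gap runs from 2.0 points (17/29 against 17/30) to 18.3 points (22/24 against 22/30).

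**GDS from Month 6 to Month 9, no subject changing status**

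1. Arm of 15, the same 12 responders seen at both visits, 1 subject missing at Month 6 and 2 at Month 9. The headline rates are 12/14 = 85.7% and 12/15 = 80.0%, a fall of 5.7 points. With observed cases at both visits they are 85.7% and 12/13 = 92.3%, a rise of 6.6 points. With missing = non-responder at both visits they are 80.0% and 80.0%.
2. All 30 subjects, 24 stable responders, the same 3 missing at both visits. The headline goes from 24/27 = 88.9% to 24/30 = 80.0%, a fall of 8.9 points. With observed cases at both visits there is no change.
3. Month 6 complete at 24/30 = 80.0%, then 3 responders miss Month 9. The headline falls to 21/30 = 70.0%; observed cases give 21/27 = 77.8%.
4. Month 6 complete at 24/30, then 3 non-responders miss Month 9. The headline stays at 24/30 = 80.0%, with no artificial fall; observed cases give 24/27 = 88.9%.

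The size, and even the presence, of an artificial fall therefore depends on who is missing and when.

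**The case against.** The strongest reply is that the rule is clear, prespecified and identical in both documents, in a descriptive pilot with no sample-size calculation. Carrying the baseline forward is a conservative convention for the primary endpoint. It need not express a belief about GAIS, which is rated against a baseline photograph and has no baseline score to carry forward. Protocol 4.4 lists relocation and schedule conflicts among reasons for withdrawal. If absence is of that kind, observed cases are unbiased and failure scoring is too low.

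There are also mitigations. Withdrawn subjects should, where possible, have a termination visit to capture secondary outcomes (Protocol 4.4), although the readable text does not say whether those values count as Month 9. SAP 2.3.1 tabulates attendance by visit, and individual data are listed, so a reader could rebuild x/N.

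Much of this stands, and it rules out four stronger readings that a reader might infer:

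- **That a subject missing at Month 9 leaves every secondary rate.** Observed-case analysis works by endpoint and visit, so she stays in the Month 6 GDS and GAIS rates.
- **That the GAIS rates are inflated as a matter of fact.** This holds only under the lack-of-effect assumption.
- **That Month 6 and Month 9 GDS cannot be compared.** The planned observed-case sensitivity analysis puts both on one rule. It removes the fall in examples 1 and 2.
- **That the 8 versus 17 mL differences are flattered.** Both arms are active, and any distortion depends on unequal missingness, for which the documents give no direction.

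The reply does not explain why one absence carries two meanings at one visit. Scoring non-response on GAIS needs no baseline value, and recalculation from listings is not a planned analysis.

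**Conclusion.** The inconsistency is real and its consequence is conditional. At Month 9 the GDS and GAIS rates rest on different denominators whenever anyone is missing, and the headline Month 6 and Month 9 GDS rates follow different rules. If the SAP's lack-of-effect assumption is correct, the observed-case secondary rates are too high, by about 4 to 18 points in an arm of 15 with 1 to 3 missing and observed rates of about 60% to 90%. If missingness is unrelated to response they are not biased, and with complete data the gap is zero. The missing counts and response rates are assumptions, and the intervals at this sample size are wide.

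The GDS trend is already partly protected by the observed-case analysis of the primary. The remaining gap is that no missing-as-failure analysis is planned for GAIS at either visit or for Month 6 GDS. For a descriptive pilot this is a modest point, but worth closing because it needs no new data.

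**What to change.** In SAP 2.4.2, keep observed cases for the secondary endpoints and add a missing = non-responder analysis on the full ITT denominator for GDS at Month 6 and for GAIS, by investigator and by subject, at Months 6 and 9. Apply it also to any between-group differences in these rates (planned in Protocol 9.4). Show the added results beside the observed-case results, with the number observed at each visit, and present Month 6 and Month 9 GDS side by side under both rules.

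The cost is a short wording change and a few repeated tables. The downside is that secondary rates under the added rule will look somewhat less favourable, and will be too low if absence turns out to be unrelated to response. That is why both versions should be shown.
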